7.6.1.1. Extreme Dose-Limiting Toxicities

In the event that any one of the following extreme DLTs is evident, the PI is to discontinue dosing study drug and study enrollment immediately, pending review by the PI, research monitor, PVG physician, and DSMB. These extreme DLTs include:

- Respiratory
 - Prolonged apnea or respiratory distress where intubation is required
- Neuropsychiatric
 - Presence of convulsions or seizure-like activity
 - Neuropsychiatric symptoms (eg, delirium, paranoia, and/or hallucinations) requiring treatment with physostigmine or other medication(s) and, in the opinion of the investigator, did not adequately respond to treatment
- Cardiovascular
 - Cardiac arrest
 - Clinically significant hypotension that requires IV fluids or vasopressors
 - Cardiac arrhythmias
 - 1^0 AV block (if the PR interval becomes \geq 280 milliseconds)
 - If the QRS duration increases by more than 25% from the pre-dose measurement and is $>$ 140 msec
 - QTc (Fridericia) is $>$ 500 msec and increase of QTc of 60 msec from baseline
 - AV block (2nd degree, 3rd degree)
 - Bundle branch block
 - Bigeminy or trigeminy associated with hypotension
 - Atrial fibrillation or atrial flutter

7.6.1.2. Nonextreme Dose-Limiting Toxicities

Nonextreme DLTs are AEs that do not meet the criteria for extreme DLTs but are serious conditions that require immediate medical attention and monitoring. The incidence and severity of these events will be used to determine whether (1) the total cohort size will be increased from 8 to 12 and (2) the need to suspend dosing until the DSMB has completed a safety review and made a recommendation to the sponsor ([Table 6](#)). Nonextreme DLTs include:

- Respiratory
 - Spontaneous respiratory rate < 8 or > 25 breaths per minute, with oxygen saturation less than 90%, which cannot be explained by agitation or other behavioral symptoms and that does not respond immediately to oxygen supplementation via nasal cannula or face mask but for which there is recovery without sequelae prior to the need for intubation
 - Dyspnea at rest
 - Symptomatic bronchospasm
- Neuropsychiatric
 - Neuropsychiatric symptoms (eg, delirium, paranoia, and/or hallucinations) requiring treatment with physostigmine or other medication(s) and, in the opinion of the investigator, responded adequately to treatment
 - Persistent neuropsychiatric symptoms, defined as a score of 4 or higher on any one item or a total score of 40 or higher on the BPRS assessment at the 48-hour, post-dose evaluation
 - Paresthesia that interferes with any activity
 - Athetoid movement
- Cardiac
 - Hypertension, which cannot be explained by agitation or other behavioral symptoms, requiring antihypertensive medication
 - Cardiac arrhythmias or changes that are deemed clinically significant but do not cause the subject to be hemodynamically unstable
 - QTc is > 450 msec for males or > 470 msec for females and has increased > 60 msec from baseline
 - Supraventricular tachycardia alone without hemodynamic compromise
 - Bigeminy or trigeminy not associated with hypotension
- Renal
 - Increase of serum creatinine by ≥ 0.3 mg/dL (≥ 26.4 μ mol/L) or increase to $\geq 150\%$ from baseline or urine output < 0.5 mL/kg/hour for > 6 hours
- Injection Site Reaction

- Any reaction determined to be severe, as defined by the FDA's guidance for injection site reactions ([Appendix B](#)).

7.6.1.3. Serious Adverse Events

In the event of an SAE that has not already been designated as a DLT but has been determined by the PI, research monitor, and PVG physician to be possibly, probably, or definitely related to the study drug, the PI is to discontinue dosing study drug and study enrollment immediately until the DSMB has completed a safety review and made a recommendation to the sponsor. The sponsor must concur with the recommendation and notify the investigator(s) before enrollment can be resumed (see Section [11.2.2](#) for SAE criteria.)

Table 6: Progression of Dosing Related to Dose-Limiting Toxicity Events

Dose-Limiting Toxicity	Number of Subjects	Action	Follow-up
Extreme DLT	1	Dosing and enrollment halted	PI, research monitor, PVG physician, and DSMB review; sponsor determines whether trial should continue
Nonextreme DLT	1 of first 4 in a cohort (or 2 in the first 8)	Dosing halted	PI, research monitor, PVG physician, and DSMB review; sponsor determines whether to increase cohort size from 8 to 12
	2 of the first 4 in a cohort (or 3 total)	Dosing and enrollment halted	PI, research monitor, PVG physician, and DSMB review; sponsor determines whether trial should continue
SAE Not Already Designated as a DLT (except unrelated)	1	Dosing and enrollment halted	DSMB to make recommendation to sponsor whether trial should continue

In summary, if any one subject has an extreme DLT, enrollment and dosing will be halted pending review by the PI, research monitor, PVG physician, and DSMB. In making its determination, the DSMB will review all relevant data and obtain additional input as needed. As a guideline to the DSMB, it is suggested that if a nonextreme DLT is observed that the DSMB consider an increase in the cohort sample size from 8 to 12 if one nonextreme DLT is observed in the first 4 subjects or 1 or 2 nonextreme DLTs are observed in the first 8 subjects and that enrollment be halted if nonextreme DLTs are observed in 2 of the first 4 subjects in a cohort or in a total of 3 subjects at any time.

If an SAE occurs at any time that is not already designated as an extreme or nonextreme DLT, unless it is reported as **unrelated** to the study drug, enrollment and dosing will also be halted pending review by the DSMB. While the presence of any specific AE may not necessarily halt enrollment, careful reporting of these events is necessary. After thorough review by the DSMB and consultation with the investigators, a decision will be made by the sponsor whether to proceed with the dosing escalation.

If any of the above events occurs, administration of investigational product will be discontinued until a thorough review of the events is undertaken by the investigators, local Institutional Review Board (IRB) and/or [REDACTED]

[REDACTED], research monitor, and/or sponsor's safety office [REDACTED]. The study may be resumed with the concurrence of the research monitor, PVG physician, sponsor's representative, PI, and the FDA.

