7.6.1. Safety Criteria for Dose Adjustment or Stopping Doses

For the purposes of determining continued dosing within a cohort or dose escalation to a subsequent planned cohort, stopping rules are based on the emergence of DLTs. Nonextreme and extreme DLTs will be considered related AEs/serious adverse events (SAEs) and will be recorded/reported as such.

Dosing of study drug and study enrollment will be halted (temporarily or permanently) as follows:

- Occurrence of any extreme DLT (dosing and enrollment to be halted immediately; PI, research monitor, PVG physician, and DSMB will review and make a recommendation to the sponsor, which will determine if dosing and enrollment may continue);
- Emergence of a specified number (see [Table 6](#)) of nonextreme DLTs among subjects in a particular dosage group (DSMB will review to determine whether dosing and enrollment may continue);
- Occurrence of an SAE not already designated as an extreme or nonextreme DLT, determined to be possibly, probably, or definitely related to the investigational product; dosing and enrollment to be halted immediately until the DSMB has completed a safety review; and

- Sponsor, DSMB, or PI's clinical judgment warrants stopping based on ongoing review of the safety profile.

The maximum tolerated dose will be the highest dose at which none of the following has been observed:

- An extreme DLT in any one subject;
- A nonextreme DLT in 2 of the first 4 subjects or in 3 subjects at any time; and
- Any SAE, not already categorized as a DLT that is considered to be possibly related, probably related, or definitely related to the study drug.

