11. SAFETY ASSESSMENT

Safety monitoring will be conducted throughout the study; therefore, safety concerns will be identified by continuous review of data by the PI, clinic staff, clinical trial monitor, research monitor, and [REDACTED].

Study Safety Management: The PI, research monitor, [REDACTED] PVG physician, and IRB will review any safety concern.

An independent DSMB is required for this study. The DSMB will be convened to review safety data and provide recommendations to the sponsor's representative. Prior to any data being provided to the DSMB, it must be reviewed and approved for release by a study biostatistician in collaboration with the [REDACTED] biostatistician. The DSMB will review cumulative study data during scheduled in-process and ad hoc reviews to evaluate safety, study conduct, and the scientific validity and integrity of the trial. After each review of study data, the DSMB will make a recommendation to the sponsor's representative. DSMB recommendations will be documented and provided in writing (via the DSMB Chair Recommendation Form) to the [REDACTED] [REDACTED]. The sponsor's representative will then decide whether to continue, modify, or suspend the study. The [REDACTED] will communicate the final decision to the investigator, who in turn will notify the IRB as appropriate. The [REDACTED] regulatory affairs scientist will communicate the final decision to the FDA, as appropriate. A description of the DSMB's roles and responsibilities, functions, reporting requirements, meeting frequency, and the study stopping/continuation criteria is included in the DSMB charter.

Research Monitor: The DoD research monitor is responsible for overseeing the safety of the research and reporting observations/findings to the IRB or a designated institutional official. The research monitor will review all unanticipated problems involving risks to subjects or others associated with the protocol and provide an independent report of the event to the IRB. The research monitor may discuss the research protocol with the investigators; shall have authority to stop a research protocol in progress, remove individual human subjects from a research protocol, and take whatever steps are necessary to protect the safety and well-being of human subjects until the IRB can assess the research monitor's report; and shall have the responsibility to promptly report his or her observations and findings to the IRB or other designated official and the [REDACTED].

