In addition to the responsibilities above, the research monitor is required to review and provide an unbiased written report for all SAEs and subject deaths to the [REDACTED] within 24 hours of his or her awareness of the event. The report provided must include, at a minimum, a brief summary of the research monitor's review of the event and event outcome, relationship of the event to the investigational product, and whether the research monitor concurs with the details of the study investigator's SAE report.

The PI (or designee) will report SAEs to the DoD research monitor. Upon receipt of an SAE report (initial or follow-up), the DoD research monitor will provide the unbiased written report using the [REDACTED] Research Monitor Report Form for each assessment. The DoD Research Monitor's report may be submitted to the [REDACTED] by the Research Monitor or the PI.

Multiple follow-up reports may be necessary for a single event, depending on when additional information becomes available. The PI (or designee) will also report all events that meet extreme and non-extreme DLT criteria, unanticipated problems, and other events with the potential to impact a subject's clinical care to the research monitor. The occurrence of any DLT(s) would result in the immediate discontinuation of dosing and study enrollment, pending a review of study data by the PI, research monitor, PVG physician, the DSMB, and the sponsor.

Medical Monitor: The medical monitor's role is separate and distinct from that of the research monitor. The medical monitor is available to serve as a resource to the clinical site and may provide consultations relating to issues such as general conduct of the study, subject eligibility, or potential protocol exceptions. The medical monitor may discuss with on-site medical staff any clinical situations that arise and provide recommendations. After the first day of dosing for each cohort, the medical monitor will review safety data with the PI to determine if it is safe to proceed with dosing the remaining subjects. The medical monitor may also perform additional tasks such as reviewing safety data listings for identification of data trends.

[REDACTED] : The [REDACTED] is responsible for the review of safety data regarding The Surgeon General, Department of the Army (TSG-DA)-sponsored products. The [REDACTED] reviews all safety events and follows them until resolution.

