[REDACTED] **PVG Physician:** The [REDACTED] PVG physician, as delegated by the sponsor, evaluates all safety cases and provides the final determination on relatedness and expectedness to the product, and whether expedited reporting is warranted per current FDA regulation and guidance.

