11.3. Relationship to Investigational Product

The investigator must assign a relationship of each AE to the receipt of the investigational product. The investigator will use clinical judgment in conjunction with the assessment of a plausible biologic mechanism, a temporal relationship between the onset of the event in relation to receipt of the investigational product, and identification of possible alternate etiologies including underlying disease, concurrent illness, or concomitant medications. The following guidelines should be used by investigators to assess the relationship of an AE to study product administration. **ONLY A PHYSICIAN CAN MAKE THIS DETERMINATION.**

Not related: No relationship to investigational product. Applies to those events for which evidence exists that there is an alternate etiology.

Unlikely: Likely unrelated to the investigational product. Likely to be related to factors other than investigational product but cannot be ruled out with certainty.

Possible: An association between the event and the administration of investigational product cannot be ruled out. There is a reasonable temporal association, but there may also be an alternative etiology such as the subject's clinical status or underlying factors including other therapy.

Probable: There is a high degree of certainty that a relationship to the investigational product exists. There is a reasonable temporal association, and the event cannot be explained by known characteristics of the subject's clinical state or factors including other therapy.

Definite: An association exists between the receipt of investigational product and the event. An association to other factors has been ruled out.

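### The trigger sentence in Protocol 7.6.1.3 makes the halt for a non-DLT SAE wait on a three-party relatedness finding, while Table 6, the text after it and the SAP halt by default

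*Protocol*

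**What the plan says.** The halt for a non-DLT SAE is stated in several places.

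- **Protocol 7.6.1.3, opening sentence.** The PI stops dosing and enrollment immediately when the SAE "has been determined by the PI, research monitor, and PVG physician to be possibly, probably, or definitely related to the study drug".
- **Protocol 7.6.1, list of halting conditions.** The SAE is "determined to be possibly, probably, or definitely related to the investigational product; dosing and enrollment to be halted immediately". No assessor is named.
- **Protocol Table 6 (inside 7.6.1.3).** The row label is "SAE Not Already Designated as a DLT (except unrelated" (closing bracket not shown). One event halts dosing and enrollment.
- **Protocol 7.6.1.3, text after Table 6.** "If an SAE occurs at any time that is not already designated as an extreme or nonextreme DLT, unless it is reported as" unrelated, dosing and enrollment stop pending DSMB review. The text does not say whose report counts.
- **SAP 3.3.1 and SAP Table 3.** These follow Table 6: any such SAE halts, with only unrelated ones exempt.

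Relatedness itself is covered elsewhere. Protocol 11.3 has the investigator assign it on a five-level scale: *Not related*, *Unlikely*, *Possible*, *Probable*, *Definite*. *Unlikely* is defined as "Likely unrelated to the investigational product. Likely to be related to factors other than investigational product but cannot be ruled out with certainty". Under Section 11 the PVG physician "evaluates all safety cases and provides the final determination on relatedness and expectedness to the product". The research monitor files a separate report within 24 hours of awareness, covering the "relationship of the event to the investigational product, and whether the research monitor concurs with the details of the study" investigator's report.

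**The concern.** A stopping rule should give one answer for one event. The 7.6.1.3 sentence is the instruction addressed to the PI, and it puts a positive finding by three people ahead of the halt. It does not say what happens if they differ, who prevails, or whether dosing is paused while they decide. The other statements in the same section need no positive finding, because they halt unless the event is cleared.

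The order also runs against the protocol's own practice. For extreme DLTs (7.6.1.1) the PI stops first, and the PI, research monitor, PVG physician and DSMB review afterwards. The text after Table 6 asks for the concurrence of several parties before the study *resumes*, which is where concurrence belongs.

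At stake is whether a site working from the 7.6.1.3 sentence doses another healthy volunteer during the interval in which Table 6 already requires a stop.

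**Working it through.** No published figure is in dispute, so the check sets the texts side by side.

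| Place | Who rates | Halts when |
|---|---|---|
| Protocol 7.6.1, list | not named | at least *Possible* |
| Protocol 7.6.1.3, opening sentence | PI, research monitor and PVG physician | at least *Possible* |
| Protocol Table 6 | not named | anything except unrelated |
| Protocol, text after Table 6 | not named | not reported as unrelated |
| SAP 3.3.1 and SAP Table 3 | not named | anything except unrelated |

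**Cut-off.** On the 11.3 scale, at least *Possible* is 3 of 5 levels. Except unrelated depends on a word that is not itself a level:

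- If it means *Not related* only, 5 − 1 = 4 levels halt, and *Unlikely* is the level on which the texts disagree.
- If it also takes in *Unlikely*, which 11.3 describes as likely unrelated, 5 − 2 = 3 levels halt, and the cut-offs agree.

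**Rater.** Four illustrative cases, taking the 7.6.1.3 sentence as needing all three and the text after Table 6 as applying to the PI's report:

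1. *PI has rated Possible; the other two have not yet rated.* The 7.6.1.3 condition is not yet met. The text after Table 6 halts now. The research monitor has 24 hours from awareness, and 7.6.1.3 sets no deadline for the finding.
2. *PI and PVG physician Possible, research monitor Unlikely.* The 7.6.1.3 condition is not met. Table 6 and the text after it halt. 7.6.1 read with the PVG physician's final determination also halts.
3. *PI and research monitor Unlikely, PVG physician Possible.* The 7.6.1.3 condition is not met. 7.6.1 read with Section 11 halts. The text after Table 6 halts only if unrelated means *Not related*.
4. *All three Unlikely.* Neither 7.6.1 nor the 7.6.1.3 sentence halts. Table 6, the text after it and SAP 3.3.1 halt if unrelated means *Not related*, and do not otherwise.

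Cases 1 and 2 differ by rater whatever unrelated means. Case 4 turns entirely on that word.

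**SAP 6.4.** Its Table 8 gives upper bounds after one SAE. The upper limit of an 80% Clopper-Pearson interval with x events in n dosed is the 0.90 quantile of Beta(x+1, n−x). With x = 1 this gives 0.680 for n = 4, 0.510 for n = 6 and 0.368 for n = 9, matching the printed 0.68, 0.51 and 0.37. (For n = 2 it gives 0.949; the SAE row prints 1.0 and the extreme-DLT row 0.95, which is a separate matter.) The bound depends only on the observed count and the number dosed.

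**The case against.** The strongest reply is that the rules are cumulative. Each states a condition that triggers a halt; none says only if, and none forbids a halt when its own condition fails. Table 6 and the text after it sit inside 7.6.1.3, so a site that complies with the whole section applies the widest trigger. This stands. A reader might infer that a split rating leaves the study with discretionary stops only; the documents do not support that, because the Table 6 halt remains mandatory.

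Three further inferences also go too far:

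- **That 7.6.1.3 contradicts 7.6.1.** It does not. 7.6.1 has the same cut-off and the same immediate halt, and is only silent on who rates.
- **That unanimity is prescribed.** All three is the natural reading of the conjunction, but the sentence does not say jointly or unanimously. Section 11 could be used as a tie-break in favour of the PVG physician. What the sentence does is leave disagreement open.
- **That the SAP's upper bounds are undermined.** They are not. A second SAE before a halt would simply enter the count.

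Counting combinations of three ratings would not measure the problem either: the documents give no rate of disagreement, and such counts are not probabilities.

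The reply does not remove the difference in trigger. The PI still has to work out that a sentence addressed to the PI is overridden by the table beneath it.

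**Conclusion.** The concern holds in limited form. The opening sentence of 7.6.1.3 makes the immediate halt depend on a prior three-party finding, without a rule for disagreement or an interim hold. Table 6, the text after it and SAP 3.3.1 halt by default, and Section 11 places the final relatedness call with one person. That rater conflict exists on either reading of unrelated. The cut-off conflict, 3 levels against 4, exists only if unrelated means *Not related*.

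Severity is minor. DLT halts are unaffected. Under 7.6.1 the sponsor, DSMB or PI may stop on clinical judgment, and the research monitor "shall have authority to stop a research protocol in progress". No analysis result changes. The conclusion assumes that the DSMB charter, which Section 11 says also holds stopping criteria and which is not among the documents, does not already settle the matter for the site.

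**What to change.** State one rule in Protocol 7.6.1, the 7.6.1.3 sentence, Table 6 and the text after it, in SAP 3.3.1 and SAP Table 3, and in the SAE row label of SAP Table 8:

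> Dosing and enrollment halt immediately on any non-DLT SAE unless the investigator reports it as Not related, and also if the research monitor or PVG physician rates it Possible, Probable or Definite. The research monitor, PVG physician and DSMB review relatedness during the hold.

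This keeps the Table 6 default, settles *Unlikely* by naming the exempt level, and covers the case where the investigator clears an event that another assessor does not.

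The maximum-tolerated-dose definition in 7.6.1 should keep its narrower cut-off (*Possible*, *Probable* or *Definite*) and say that the PVG physician's final determination is the one used. Otherwise an SAE that caused only a precautionary pause could be taken to limit the dose.

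The cost is one rule repeated in these places and one added clause. No new data are needed, because 11.3 and Section 11 already require all three assessments. The downside is an occasional short pause for an SAE later found unrelated.
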